Title	
- ADEQUATE STUDY -
 
A prospective, multicenter non-interventional study to evaluate the efficacy of Enbrel® (etanercept) over a period of 12 months in the routine treatment of patients with rheumatoid arthritis, axial spondyloarthritis, psoriatic arthritis, or plaque psoriasis with particular focus on the clinical status improvements still observable after 12 weeks of treatment.

Study number:	B1801385
Version:	Final 1.3
Date:	30.01.2015
Name of active substance:	Enbrel® (etanercept)
Scientific question and goals	
The goal of this non-interventional study is to evaluate the efficacy of etanercept during routine clinical use over a maximum of 12 months in patients with rheumatoid arthritis, psoriatic arthritis, axial spondyloarthritis, or plaque psoriasis. In so doing, particular attention will be paid to the proportion of those patients who only attain the desired treatment goal after 12 weeks of treatment. The primary efficacy end point for the study is the proportion of patients who attain the desired treatment goal after 12 and 24 weeks, whereby data collection tools including DAS28, PASI, PGA, and ASDAS will be used to define the indication-specific treatment goal in accordance with the currently valid national/international treatment guidelines and -recommendations.
 
The secondary efficacy end points for the study include not only objective measures of disease activity but also patient-reported

	
information regarding function.
 
Safety and tolerability of the treatment are recorded based on the documentation of adverse events and the reasons for premature ending of treatment.

Author	[name] Pharma GmbH [name]

TABLE OF CONTENTS

TABLE OF CONTENTS	3
1. LIST OF ABBREVIATIONS	5
2. RESPONSIBILITIES	7
3. ABSTRACT	7
4. AMENDMENTS AND UPDATES	7
5. MILESTONES	7
6. RATIONALE AND BACKGROUND INFORMATION	8
6.1. Background information	8
6.2. Study rationale	8
7. SCIENTIFIC QUESTION AND GOALS	10
8. STUDY METHODS	10
8.1. Study design	10
8.1.1. Design and study procedures	10
8.1.2. Primary study end points	12
8.1.3. Secondary end points at weeks 12, 24, 36, and 52	12
8.2. Study setting	13
8.2.1. Study conduct	13
8.2.2. Inclusion criteria	14
8.2.3. Exclusion criteria	14
8.3. Variable description	14
8.4. Source documents	16
8.5. Calculation of case numbers	16
8.6. Data management	17
8.7. Data analysis	17
8.8. Quality control	17
8.9. Strengths and limitations of the study methodology used	18

1. LIST OF ABBREVIATIONS

Abbreviation	Definition
AMG	Arzneimittelgesetz [German Drug Act]
ASDAS	Ankylosing Spondylitis Disease Activity Score
AXSPA	Axial spondyloarthritis
BASDAI	Bath Ankylosing Spondylitis Disease Activity Index
BSA	Body Surface Area
ESR	Erythrocyte sedimentation rate
CDAI	Clinical Disease Activity Index
CRF	Case Report Form
CRP	C-reactive protein
CSR	Clinical Study Report
DAS	Disease Activity Score
DLQI	Dermatology Life Quality Index
DSU	Drug Safety Unit
DVP	Data Validation Plan
EIU	Exposure in Utero
ETN	Etanercept
EULAR	European League Against Rheumatism
FDAAA	Food and Drug Administration Amendments Act
FFbH	Hannover Functional Questionnaire
GCP	Good Clinical Practice
GPP	Good Pharmacoepidemiology Practice
IEC	Independent Ethics Committee
IRB	Institutional Review Board
ISPE	International Society for Pharmacoepidemiology
ISPOR	International Society for Pharmacoeconomics and Outcomes Research
LDAS	Low Disease Activity Score
LSLV	Last Subject Last Visit
MDA	Minimal Disease Activity
MTX	Methotrexate
PASI	Psoriasis Area and Severity Index
PCD	Primary Completion Date
PhRMA	Pharmaceutical Research and Manufacturers of America
PRO	Patient-Reported Outcome(s)

PsA	Psoriatic Arthritis
PSARC	Psoriatic Arthritis Response Criteria
PsO	Plaque Psoriasis
RA	Rheumatoid Arthritis
RF	Rheumatoid Factor
SAP	Statistical Analysis Plan
SDAI	Simple Disease Activity Index
SAE	Serious Adverse Event
AE	Adverse Event
VAS	Visual Analog Scale

3. ABSTRACT

An abstract is not required.

4. AMENDMENTS AND UPDATES

Currently not applicable.

5. MILESTONES

Milestone	Planned date
Start of data collection	01. February 2015
End of data collection	31. July 2017
Final study report	30. June 2018

6. RATIONALE AND BACKGROUND INFORMATION

6.1. Background information

For patients with rheumatic diseases, attaining remission or at least low disease activity and close monitoring result in more favorable statuses which are visible in radiology findings and functionally measurable [1-3]. If remission cannot be attained, at least a low level of disease activity should be achieved, as is often the case especially with a long-persisting disease. The German treatment guidelines for rheumatoid arthritis indicate that the desired treatment goal should be attained after 3 months and in any case after no more than 6 months [4]. The same approach also applies accordingly for other indications.

For psoriatic arthritis (PsA), criteria according to PSARC and the extent of body surface area (BSA) affected are also used to assess disease activity in patients with PsA [5]. For axial spondyloarthritis (axSpA), the most proven parameters for the assessment of disease activity are ASDAS or BASDAI [6]. The assessment of disease activity in plaque psoriasis (PsO) is usually performed using PASI, BSA, and DLQI [7, 8].

The COMET study has shown that RA patients who start treatment with etanercept early on are more likely to attain clinical remission. In this study, the DAS remission criteria were attained after 24 weeks by 50 % of the patients, which constituted a further 40 % increase versus the status attained at week 12. After 52 weeks, 57 % of the patients had attained the remission criteria [9].

In the PRISTINE study, Strohal was able to show that 37.2 % of the patients with PsO who were treated once weekly had attained a PASI75 after 12 weeks (62.4 % when treated with 50 mg twice weekly). The number of patients who attained a PASI75 increased to 59.9 % after 24 weeks (78.2 % when treated with 50 mg twice weekly) [10].

These studies show clearly that it may be worth continuing treatment with etanercept beyond 12 weeks even if the criterion for low disease activity has not yet been attained.

6.2. Study rationale

Approx. 20 - 30 % of patients end their treatment with etanercept during the first year of treatment, whereby the discontinuation of treatment is due to a lack of efficacy or side effects. The German and also the EULAR guidelines for the treatment of RA recommend a change of treatment after 3 and at most after 6 months if the criterion for low disease activity has not been attained [4, 11, 12]. The treatment guidelines for the other indications for which etanercept is approved are similar.

Clinical studies in the indications of RA, axSpA, PsA, and PsO show that it may be worth continuing treatment beyond a period of 12 weeks even if the criterion for low disease activity has not yet been attained, because the number of patients who only attain this criterion beyond the 12 weeks is increasing.

In routine care, according to national and EULAR guidelines, the medical assessment of the treating rheumatologist or dermatologist and other criteria should be taken into consideration in addition to the purely numerical assessment of treatment goals. Therefore, the assessment as to whether the treatment goals were ultimately attained depends in everyday clinical practice not only on the numerical results from the DAS, ASDAS (or PSARC) or PASI tools, but also on the overall evaluation of the physician and the patient, as well as on the treatment outcomes reported by the patient ("patient reported outcomes," PRO), treatment satisfaction, and other social and functional factors.

In summary, it is therefore the primary goal of this study to check how many patients in everyday clinical practice benefit from the continuation of treatment with etanercept beyond 12 weeks, even if the defined treatment goal has not yet formally been attained at that time but treatment is continued based on the judgment of the prescribing physician and the patient. In so doing, this rate is to be compared across the different indications. The variables which also reflect compliance with the treatment guidelines by physicians are to be examined in terms of additional influencing factors such as disease duration, concomitant medications, or PROs.

Early treatment with biologics is recommended for all indications in order to attain improved quality of life and patient function and to exert a favorable effect on comorbidities, e.g. cardiovascular diseases. It is not yet known whether the burden of disease is comparable in the different indications at the start of treatment with etanercept. Here, a better understanding of these relationships could help doctors to determine the optimal time point for the start of treatment with etanercept.

In this study, the variables are examined in a joint study setting (as far as is currently known, for the first time), which permits these variables to be compared directly across the different indications. Even though the treatment goals and the extent of disease activity in the different indications are determined based on different tools, it will still be possible to measure and compare PROs in particular, such as global assessment, pain, fatigue, mental health and - at least for the rheumatological indications - FFbH (comparable with the HAQ) and morning stiffness, regardless of the indication. The overall physician's assessment will also be measured in all indications and compared between the individual indications.

In addition to findings regarding relevance to practice and the reality of care according to treatment guidelines and recommendations, patient compliance with the treatment plan will be scientifically studied in detail.

The goal of Pfizer's own "TOGETHER" program is to improve patient treatment compliance with training measures. This study is to investigate the extent to which participation in the "TOGETHER" program influences treatment compliance.

7. SCIENTIFIC QUESTION AND GOALS

The primary goal of this study is to determine how many patients treated under everyday conditions benefit from the continuation of treatment with etanercept beyond 12 weeks even if the desired treatment goal (see Table 2) has not yet been attained at that time point, as well as to compare these rates across the different indications. For this purpose, the following questions are to be answered based on a reliable data body collected during clinical routine:

- Proportion of patients who have not attained defined treatment goals for each respective indication after 12 weeks, but do attain these between weeks 12 and 24.
- Proportion of patients who have attained the desired treatment goal after 12 weeks,
- Proportion of patients who continue treatment up to week 52 in the different indications,
- Comparison of PRO results across indications,
- How is the decision made in everyday clinical practice whether treatment with etanercept is continued or discontinued (i.e. which other parameters are taken into consideration, for example PRO or physician's global assessment),
- At what time point is the decision made to switch treatment (i.e. after 3 or 6 months, or even later),
- Are there predictive factors for the continuation of treatment with etanercept,
- What factors may influence treatment compliance (e.g. participation of the patients in a compliance program).

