8. STUDY METHODS

8.1. Study design

8.1.1. Design and study procedures

This study is a prospective, multicenter, non-interventional study to evaluate the efficacy of etanercept in patients with RA, PsA, axSpA or PsO.

Efficacy data will be documented within a period of 12 months and health outcomes every quarter in the course of routine treatment. An overview of the documentation to be performed can be found in Table 1 below.

Table 1: Overview of study procedures					
	Visit 1 Week 0	Visit 2 Week 12	Visit 3 Week 24	Visit 4 Week 36	Visit 5 Week 52
Medical history	X				
Inflammation in MRI (axSpA)	X				
Radiological Sacroiliitis (axSpA)	X				
Participation in the “Together” program	X				
Inclusion/exclusion criteria	X				
Treatment/medications					
Prior treatment	X				
Treatment with Enbrel	X	X	X	X	X
Concomitant treatment		X	X	X	X
Safety parameters					
Physical examination	X				
Laboratory	X	X	X	X	X
AE documentation		X	X	X	X
Efficacy					
Examination of joints	X	X	X	X	X
PASI (PsO)	X	X	X	X	X
Morning stiffness (RA, axSpA, PsA)	X	X	X	X	X
Patient and physician global assessment	X	X	X	X	X
Pain	X	X	X	X	X
Fatigue	X	X	X	X	X
Occiput-to-wall distance (axSpA)	X	X	X	X	X
Dactylitis (PsA)	X	X	X	X	X
Nail involvement (PsO, PsA)	X	X	X	X	X
Enthesitis (PsA, axSpA)	X	X	X	X	X
Pruritus (PsO)	X	X	X	X	X
Health outcomes					
FFbH (RA, axSpA, PsA)	X	X	X	X	X
BASDAI (axSpA)	X	X	X	X	X

DLQI (PsO)	X	X	X	X	X
PHQ-2	X	X	X	X	X

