8.1.2. Primary study end points

- Patients with RA: Proportion of patients who attain the desired treatment goals (see Table 2) at the week 12 and week 24 time points under monotherapy or in combination with MTX and maintain these long-term over a period of 52 weeks.
- Other indications: Proportion of patients who attain the desired treatment goals according to guidelines (see Table 2) in each respective indication at the week 12 and week 24 time points.

8.1.3. Secondary end points at weeks 12, 24, 36, and 52

All patients:

- Proportion of patients who continue treatment with etanercept,
- Occurrence of adverse events,
- Remission,
- Patient global assessment,
- Fatigue,
- Pain (VAS),
- Physician global assessment,
- PHQ-2
- Comparison of the parameters “patient global assessment,” “fatigue,” “pain,” “physician global assessment,” and “PHQ-2 across all indications,
- Comparison of FFbH and morning stiffness among patients with RA, axSpA, and PsA,
- Discontinuation of treatment due to a lack of efficacy or adverse events,
- Nature of further treatment if treatment has been discontinued,

Additionally for RA patients:

- FFbH
- CDAI
- SDAI

Additionally for axSpA patients:

- BASDAI,
- FFbH
- Enthesitis
- Occiput-to-wall distance

Additionally for PsA patients:

- BSA

- Dactylitis
- Enthesitis
- FFbH

Additionally for PsO patients:

- PASI, median time to PASI75, body segment (head, trunk, upper and lower extremities) and component-related subscales (erythema, induration, flaking) over 24 weeks,
- DLQI,
- Pruritus
- BSA.

The following indication-related laboratory tests will be documented if they are available as part of a routine assessment:

- Erythrocyte sedimentation rate (ESR), C-reactive protein (CRP)

In addition, the following laboratory tests will be documented for patients with RA, PsA, and axSpA if they are available as part of a routine assessment:

- Rheumatoid factor (RF) and anti-CCP antibodies.
- HLA-B27 at Visit 1 (just axSpA).

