8.3. Variable description

The primary and secondary end points are listed in section 8.1.2 and section 8.1.3.

All of the indication-specific efficacy measures used in this study, such as DAS28, BASDAI or PASI, are clearly defined and meet the current international scientific standard. The definitions for “desired treatment goals” in the individual indications were based on recommendations, including from national and international treatment guidelines. An overview of these recommendations can be found in Table 2 below.

Table 2: Overview of desired treatment goals and minimum efficacy criteria in the different approved etanercept indications, based on the current latest treatment guidelines

Indication	Desired treatment goal	Minimum efficacy	Source
PsO	
 • PASI75 or • PGA (“clear” or “almost clear”) and • DLQI 0 or 1 	
 • PASI50 and • DLQI <5 or improvement of at least 5 points 	S3 Guidelines for the systemic treatment of PsO [7, 8]
RA	
 • DAS28 <2.6 	
 • DAS28 \leq3.2 or • Physician assessment, e.g. based on radiology findings 	S1 Guidelines of the DGRh [4]
axSpA	
 • ASDAS <1.3 	
 • BASDAI: 50% relative difference or absolute difference of 2 points (scale from 0 -10) and • Expert opinion on continuation: yes/no 	Kiltz et al. 2014 [13]
PsA	
 • DAS28 <2.6 or • MDA criteria met^a 	
 • DAS28 \leq3.2 or • Physician assessment, e.g. based on radiology findings 	a) Mease 2011 [5]

Selected parameters, such as remission, low disease activity, or continuation of treatment, will be analyzed for potential influencing variables (e.g. duration of disease, clinical outcomes, PRO).

Detailed information on the calculation of variables and on data evaluation in general will be set forth in a separate statistical analysis plan (SAP) before the start of the evaluation.

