8.5. Calculation of case numbers

It is assumed that the RA patients included in this study who are receiving a combined treatment (ETN + MTX) will be similar to those patients included in the randomized, double-blind DOSERA study in terms of the proportion of patients continuing treatment beyond week 12 (i.e. adequate efficacy - defined based on the DAS28 and the patient and physician global assessment of disease progression - has been attained). In that study, 22 - 26 % of the patients on combined treatment had attained no adequate efficacy after 12 weeks and continued treatment with etanercept (open-label), while conversely, adequate efficacy from treatment had been attained for 74 - 78 % of the patients at week 12. The sample size for this non-interventional study was calculated with the primary focus on the indication of RA.

Assuming that 74% of the patients under treatment with ETN + MTX and 66% of the patients under ETN monotherapy exhibit adequate response to treatment after 12 weeks (odds ratio of 0.682), 1200 patients (with a 2:1 ratio, this equals 800 patients under combined treatment and 400 patients under monotherapy) will be sufficient to detect a significant difference in the primary end point “proportion of patients attaining the desired treatment goal” with a power of 80% using a two-sided test with a significance level of 5%.

A logistic regression quoting the odds ratio and the corresponding 95% confidence interval is the appropriate statistical methodology for the analysis of this binary variable. As a sensitivity analysis, a GEE (generalized estimating equation) analysis can also be performed as a repeat method to obtain the binary response variable.

Because the combination with MTX is not recommended for the indications axSpA, PsO, and PsA, the inclusion of 300 patients in each of these indications appears sufficient for analysis of efficacy and tolerability.

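### Late benefit is counted as a one-way crossing at essentially one visit, with no paired loss count or persistence check, and the plan does not say whether this measure or the differing section 8.1.2 end points feed the comparison across indications

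*Combined protocol and SAP*

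**What the plan says.** Section 7 sets the primary goal: how many patients benefit from continuing beyond week 12 although the goal was missed at that point, "as well as to compare these rates across the different indications". The first question listed under it is "Proportion of patients who have not attained defined treatment goals for each respective indication after 12 weeks, but do attain these between weeks 12 and" (the upper limit is week 24). The rule is worded identically for every indication and has no maintenance condition for any of them, RA included.

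Table 1 (section 8.1.1) schedules visits at weeks 0, 12, 24, 36 and 52, so week 24 is the only planned assessment after week 12 inside the window.

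Section 8.1.2 defines the primary end points differently. For RA they are attainment at weeks 12 and 24 "and maintain these long-term over a period of 52 weeks". For the rest the text is "Other indications: Proportion of patients who attain the desired treatment goals according to guidelines (see Table 2) in each respective indication" at weeks 12 and 24, with no maintenance clause. What counts as maintaining the goal is not defined.

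Section 8.1.3, "Secondary end points at weeks 12, 24, 36, and 52", lists remission for all patients. Sections 8.3 and 8.7 leave calculation details to a separate SAP. Section 8.9 acknowledges that there is no randomised control group.

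**The concern.** The section 7 rate selects patients on the wrong side of a cut-off at week 12 and re-measures them at week 24. Where a score varies between visits, some of them will cross with no lasting improvement, while some patients at goal at week 12 will cross back. The rate counts the first group and leaves out the second. With no control arm, the natural internal checks are the paired losses and whether late attainers stay at goal. The plan asks for neither.

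This rate answers the study's main question. Read alone, it would be positive even in a population that did not change after week 12.

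The comparison across indications is exposed in two ways. Chance crossing depends on how many patients are at goal at week 12, and that share will differ between indications. In addition, the plan holds two non-matching definitions of the primary quantity and does not say which one is compared.

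**Working it through.** **1. The plan's own calculation.** Section 8.5 assumes 74% versus 66% at week 12, a 2:1 ratio, and a test "with a power of 80% using a two-sided test with a significance level of 5"%. The two-proportion formula with continuity correction gives 800 + 400 = 1200, an exact match (1146 without the correction). The odds ratio is (0.66/0.34)/(0.74/0.26) = 0.682, as stated. This sample size rests on week-12 response only, so the present point does not affect it.

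**2. Inputs for the illustration.**
- RA background (section 6.1): 50% in remission at week 24, described as a further 40% increase on week 12. If that increase is relative, week 12 is 0.50/1.4 = 35.7%. If it means points, week 12 is 50 − 40 = 10%. The relative reading is assumed below.
- PsO background (section 6.1, once-weekly group): PASI75 in 37.2% at week 12 and 59.9% at week 24.
- Correlation r between a patient's week-12 and week-24 scores: not in the documents. Assumed 0.6 to 0.95.
- Model (assumed): bivariate normal score, goal met when the score is below the cut-off.

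**3. No true change.** Let p be the proportion at goal at each visit and B(r) the proportion at goal at both. The crossing rate among week-12 non-attainers is (p − B)/(1 − p). The proportion of all patients who lose the goal is also p − B, so gains equal losses and the net change is 0.

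For p = 0.357:

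| r | B | gained = lost (all patients) | counted as late benefit among week-12 non-attainers |
|---|---|---|---|
| 0.95 | 0.310 | 4.7% | 7% |
| 0.9 | 0.290 | 6.7% | 10% |
| 0.8 | 0.262 | 9.6% | 15% |
| 0.7 | 0.239 | 11.8% | 18% |
| 0.6 | 0.220 | 13.7% | 21% |

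Example at r = 0.6: (0.357 − 0.220)/0.643 = 0.21. If week 12 were 10% instead, the last column would run from 2% (r = 0.95) to 7% (r = 0.6).

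**4. Dependence on the week-12 rate.** At r = 0.8 with no change, chance crossing is 15% when 35.7% are at goal and 32% when 74% are: (0.74 − 0.657)/0.26 = 0.32. The 74% is borrowed from section 8.5, where it refers to adequate response; it serves here only to show the dependence.

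**5. With a real improvement.** Gained minus lost equals the net rise, so the gross rate always exceeds the net change when anyone loses the goal.
- RA, 35.7% to 50% (net +14.3 points): gained 15.1 to 22.7 points, lost 0.8 to 8.4 points, for r from 0.95 to 0.6.
- PsO, 37.2% to 59.9% (net +22.7 points): gained 22.9 to 28.6 points, lost 0.2 to 5.9 points.

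Dividing the no-change crossing by the crossing with these rises gives about 31% to 61% for RA (0.0472/0.1505 to 0.1373/0.2267) and 21% to 49% for PsO (0.0479/0.2287 to 0.1393/0.2862).

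**6. Does persistence discriminate?** In a simulation with no true change, p = 0.357 and equal correlation between visits (0.7 to 0.9), only about 44% to 47% of chance crossers are at goal again at week 36. Persistence therefore filters chance crossing in part, not completely.

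**7. The two definitions side by side.** Section 7: missed at week 12, attained by week 24, same rule for all. Section 8.1.2: attained at weeks 12 and 24, with 52-week maintenance for RA alone. If the RA wording means attainment at both visits, a late attainer could never count in it. The text does not settle this.

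**The case against.** **RA disadvantaged by construction.** A reader might infer that RA must look worse than the other indications because only RA carries a maintenance condition. The documents do not support that. The section 7 measure has no such condition for any indication, and the only analysis specified for the primary end point (sections 8.5 and 8.7) compares RA combination therapy with RA monotherapy. The inference holds only if the section 8.1.2 end points are what is compared, which is left open.

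**Most of the rate is noise.** A reader might also conclude that the majority of the late-attainment rate is fluctuation. A small assumed effect gives that result: a DAS28 fall of 0.3 with SD 1.3 and correlation 0.6 to 0.8 yields 61% to 71%. None of those inputs is in the protocol. The background rises in section 6.1 give the lower and wider ranges in step 5 of the working.

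**Other checks exist.** Week-12 and week-24 proportions are primary end points in section 8.1.2, so a rough net change can be derived, and remission is reported at all later visits. This stands: losses and persistence are not the only internal checks. But separate proportions are unpaired. Section 6.2 expects 20% to 30% to stop treatment in the first year, and section 8.9 says missing observations are usually not replaced, so the two proportions may describe different patients. Remission at weeks 36 and 52 does not follow the late attainers as a group.

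**Detail belongs in the SAP.** This is fair for table layouts. The choice of what counts as benefit, and which definition is compared, is made in sections 7 and 8.1.2 and needs settling there.

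**Conclusion.** The point holds. As written, the section 7 rate mixes real late response with fluctuation, and the plan requests neither paired losses nor persistence of late attainers. How much is fluctuation cannot be derived from the documents. Under the stated assumptions (normal scores, correlation 0.6 to 0.95, no true change, about 36% at goal), 7% to 21% of week-12 non-attainers would be counted. This depends on reading the 40% increase as relative. Because chance crossing rises with the week-12 attainment rate, raw rates can differ between indications even under one rule.

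The RA-only maintenance clause is a mismatch between sections 7 and 8.1.2 that must be reconciled; it is not demonstrated bias against RA. The planned 1200 RA patients are unaffected. What is at risk is the interpretation of the headline result.

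**What to change.** In sections 7 and 8.1.2 and in the SAP:

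1. For each indication, report the paired week 12 to week 24 table (gained, lost, stayed at goal, stayed not at goal) among patients assessed at both visits, and show the net change beside the late-attainment rate.
2. For all four indications, report the proportion of week-24 late attainers still at goal at weeks 36 and 52. Show it twice: with patients who stopped or have missing data counted as not maintained, and among observed patients only.
3. State that the comparison across indications uses the section 7 late-attainment rate under one identical rule for all four, and keep the RA 52-week maintenance end point separate from it.

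The cost is wording and extra tables. The visits are already in Table 1, although section 8.1.3 records ESR and CRP only where routinely available, so goals that use them may be missing for some patients. Section 8.7 requires an amendment for a substantial change to the primary end point, so this is best settled before the SAP is final and before the interim abstracts in section 11.1. The net or sustained rate will look less favourable than the raw one.
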